Figure 2. Schematic overview of the study design of the evaluation study.

4 Study population

A total of 200 participants will be recruited for this study. The target population consists of healthy men and women aged 35 to 80 years with normal weight, overweight, or obesity.

Inclusion criteria for this study are:

- BMI ≥ 20 and < 40 kg/m².
- Age 35–80 years.
- Good command of the Dutch language.
- Reasonable digital literacy and access to a PC or laptop.
- A fairly typical Dutch dietary pattern.

Exclusion criteria for this study are:

- Pregnant women or women who are breastfeeding.
- Recent unintentional weight loss of more than 5 kg.
- Under treatment for a serious (chronic) illness.
- History of myocardial infarction or stroke in the past 5 years.
- Previous or planned bariatric surgery.

In this study, we aim to perform subgroup analyses to examine whether there are differences in the usability of the Nutri+ module between men and women, across different age groups, between low and high socioeconomic status, and between individuals with normal weight and those with overweight or obesity. The rationale for this is the known differences in dietary intake among these subgroups and the potentially higher risk of over- or underreporting. Therefore, during recruitment, we will strive for a proportional distribution of sex (male/female), age (35–55 / 55–80), educational level (primary/secondary vocational or higher education/university), and BMI (20–25 / 25–30 / 30–40) in the study population. For sex, this will already be considered during screening: once 100 participants of a particular sex are recruited, only participants of the other sex will be admitted.

Recruitment will mainly take place via social media platforms (Facebook, LinkedIn, Instagram). If necessary, recruitment will be expanded through other channels, such as local newsletters and websites (e.g., “In de Buurt”). The number of participants represents our minimum target for data collection to ensure valid and reliable outcomes and to allow for subgroup analyses. Recruitment will therefore continue until the minimum number of participants is reached; additional participants are welcome (up to a maximum of 300). There will be no reserve participants.

5 Description of the study

First Phase

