After completing the first series (autumn 2022), participants are reminded that they will be contacted again in spring 2023 to complete the Nutri+ module and Compl-Eat. The same procedures are followed in spring 2023 as in autumn 2022.

Participants are also asked to complete an evaluation questionnaire regarding their experiences with completing the questionnaire and the visualization of the dietary profile wheel.

After data collection for the evaluation study is completed, the data are analyzed. Based on this analysis, recommendations will be made for adjusting the Nutri+ module (questionnaire, algorithms, and cut-off values) and for improving the visualization of the profile wheel.

Tabel 2: Overview timeline and investment for participants evaluation study

	How often and when	Total time investment
--	--------------------	-----------------------

Nutri+ module	1 time filling out autumn 2022 1 time filling out spring 2023	2 times, 20 minutes. 40 minutes in total.
Compl-eat	1 time 4 days filling out autumn 2022 1 time 4 days filling out spring 2023	80 minutes per time. 160 minutes in total.
Evaluation questionnaire	1 time filling out	15 minutes

6 Outcome variables

To evaluate the Nutri+ module in comparison with Compl-Eat, it is first necessary to assess the extent to which the food groups used in the Nutri+ module are also available in Compl-Eat. The outcomes listed below depend on the results of this mapping. In addition, Compl-Eat will need to apply the same food group classification based on the same cut-off values per product group as used in the Nutri+ module.

Primary outcomes

- Intake in grams for the 17 product groups that are quantitatively assessed (Fruit, Vegetables, Legumes, Nuts and Seeds, Fish, Dairy, Meat, Eggs, Soft Drinks, Alcohol, Coffee, Tea, Snacks, Sweet Spreads, Chips/Nuts/Party Snacks, Fast Food, Desserts/Ice Cream/Cakes) for both Compl-Eat and the Nutri+ module.

Secondary outcomes

- Evaluation overall and by subgroup (sex, BMI, etc.) for all product groups available in both Compl-Eat and the Nutri+ module, for which guidelines exist to assess reproducibility and classification. For Nutri+, these include: Fruit, Vegetables, Butter and Cooking/Frying Products, Dressings and Oils, Legumes, Nuts and Seeds, Fish, Dairy, Meat, Eggs, Cereal Products, Potatoes, Soft Drinks, Alcohol, Coffee, Tea, Snacks, Sweet Spreads, Chips/Nuts/Party Snacks, Fast Food, Desserts/Ice Cream/Cakes.
- Energy intake based on Compl-Eat

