- Expected energy intake based on sex, age, weight, and physical activity
- Evaluation of the profile wheel

7 Description of incidents, safety, adverse events, side effects

The study for participants consists of completing dietary questionnaires and 24-hour dietary recalls. Due to the nature of the study, no incidents or adverse events are expected. Any complaints regarding the conduct of the study, the websites used, or other questions or remarks can be submitted via email or telephone, as indicated in the participant information.

8 Data-analysis and statistics

For Compl-Eat, all analyses will be based on the average intake per product group across the four assessment days within a single measurement series (spring or autumn).

Based on the Compl-Eat data, it will be assessed whether there is excessive under- or over-reporting in the study population. To this end, the number of calories consumed, as calculated by Compl-Eat, will be compared with the expected caloric intake based on participants' age, sex, height, and weight.

The agreement between classifications in Compl-Eat and the Nutri+ module will be evaluated by assessing the percentage overlap in categorization and subsequently examining correlations between the scores. The goal is for 75% agreement per product group between the Nutri+ module and Compl-Eat. If lower agreement is observed, the data will be qualitatively examined to identify areas for improvement in the Nutri+ module.

In addition, the intake in grams per product group as measured by the Nutri+ module and Compl-Eat will be examined. Correlation coefficients will be calculated to assess agreement between the Nutri+ module and Compl-Eat. These outcomes are primarily exploratory and aim to provide insight into where the largest differences between Compl-Eat and Nutri+ occur. These insights can be used to further improve the Nutri+ module.

To assess the reproducibility of the Nutri+ module, correlations between the spring and autumn measurements will be used.

Participants' opinions on the visualization of the profile wheel will be evaluated using descriptive information.

9 Risk analysis relating to the conduct of the study

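### The subgroup evaluation includes no signed Nutri+ versus Compl-Eat difference, so it is poorly placed to show the subgroup over- or under-reporting that helps to justify it

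*Combined protocol and SAP*

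**What the plan says.** Section 4 (Study population) plans subgroup analyses of the module's usability by sex, age, socioeconomic status and weight class. It explains why: "The rationale for this is the known differences in dietary intake among these subgroups and the potentially higher risk of over- or underreporting". The recruitment target is tied partly to these analyses. "A total of 200 participants will be recruited for this study", and "additional participants are welcome (up to a maximum of 300"). For sex, "once 100 participants of a particular sex are recruited, only participants of the other sex will be admitted". Age, education and "BMI (20–25 / 25–30 / 30–40") are to be balanced as far as possible.

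Section 6 (Secondary outcomes) is the only place that attaches an outcome to the subgroups: "Evaluation overall and by subgroup (sex, BMI, etc.) for all product groups available in both Compl-Eat and the Nutri+ module". The same entry limits this to certain groups and states its purpose: those "for which guidelines exist to assess reproducibility and classification". The primary outcome, grams for 17 product groups from both methods, has no subgroup element.

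Section 8 (Data-analysis and statistics) names no subgroup method. Classification is "evaluated by assessing the percentage overlap in categorization and subsequently examining correlations between the scores". Grams and reproducibility are analysed by correlation. The misreporting check compares Compl-Eat energy with expected energy for the whole study population, so it examines neither Nutri+ nor subgroups. The main objective in Section 2 mentions the share of Compl-Eat intake that Nutri+ captures, but not by subgroup.

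**The concern.** Over- or under-reporting by Nutri+ in a subgroup is a signed shift in grams. Neither statistic that the plan links to subgroups measures such a shift. A correlation does not change if everyone in a subgroup reads low by the same proportion. Percentage overlap counts matches between colours and ignores the direction of the mismatches. It also depends on how many people sit near a cut-off, so subgroups with different intakes, which Section 4 expects, can differ in overlap when Nutri+ measures them equally well.

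Section 5 says that the results will lead to recommendations on the questionnaire, algorithms and cut-off values. A real subgroup bias could go unseen. Conversely, a gap in overlap that only reflects intake level could be taken as a reason to change the module.

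**Working it through.** **The plan's own figure.** The target of 200 cannot be reproduced, because no alpha, power, effect size or SD is given. What follows is what 200 implies.

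**Inputs from the documents.** 100 v 100 for sex (Section 4). Colour cut-offs at 50% of the recommended amount and at roughly meeting the guideline, modelled as 100%. Agreement goal 75% per product group (Section 8).

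**Assumptions.** Two-sided 5%, no dropout. Log usual intake is normal with SD 0.6. Each method adds independent normal error on the log scale with SD e = 0.2, 0.3 or 0.4. Median intake is 61%, 70%, 100% or 135% of the guideline. Nutri+ reads 20% low in one subgroup only, a shift of ln 0.8 = −0.223. Compl-Eat is unbiased.

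**1. Overlap without the intake model.** From a base of 75% agreement, 100 v 100 has 12% power for a fall to 70% and 34% for a fall to 65%. The fall detectable with 80% power is to about 56%. It is about 55% at 67 v 133 (normal weight v the rest, if the three BMI strata fill evenly) and about 60% at 150 v 150 (300 split evenly).

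**2. Overlap with a 20% bias.** Power = Φ((d − 1.96·s0)/s1), where d is the difference in agreement, s0 = √(2p̄(1−p̄)/100) and s1 = √((p1(1−p1) + p2(1−p2))/100). Example: e = 0.3, median 100% of guideline. Agreement is 68.7% without bias and 63.3% with it. So d = 0.054, s0 = s1 = 0.067, and Φ((0.054 − 0.131)/0.067) = Φ(−1.15), about 13%.

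**3. Log ratio of grams with the same bias.** The SD of log(Nutri+/Compl-Eat) is √2·e. The noncentrality is 0.223/(√2·e·√(2/100)) = 0.223/(0.2e), which gives 5.58, 3.72 and 2.79.

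| Error SD per method | Overlap, range over medians | Signed colour difference | Log ratio of grams |
|---|---|---|---|
| 0.2 | 14–26% | 86–92% | >99% |
| 0.3 | 6–16% | 68–75% | 96% |
| 0.4 | 5–12% | 51–57% | 79% |

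The signed column compares the mean number of colour steps by which Nutri+ sits above or below Compl-Eat.

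**4. Opposite biases.** One subgroup 20% low, the other 25% high, median 70% of guideline, e = 0.3. Agreement is 62% in both, so overlap shows nothing. Nutri+ gives a lower colour in 30% and a higher one in 8% of the first subgroup; the second is the reverse.

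**5. Correlation.** Adding a constant to log intake, or multiplying grams by a constant, leaves a correlation unchanged. In simulation, a constant 20% bias in one subgroup led to the retest correlations being declared different 4.7% of the time, which is the false-positive rate.

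**6. Intake level alone, no bias, e = 0.3.** Agreement is 68.7% at a median of 100% of the guideline and 75.6% at 135%; at 100 v 100 this gap would be flagged about 19% of the time. At 80% v 160% of the guideline, agreement is 65.9% v 80.3%, flagged about 64% of the time. With log intake SD 0.5 it is 62.5% v 80.7%, flagged 82–83% of the time, while the log-ratio comparison rejects 4.6% of the time.

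**7. Sensitivity.** At e = 0.5, overlap has 5–10% power and the log ratio 60%. Over a wider grid (log intake SD 0.5–0.7, e = 0.2–0.5, medians 40–180% of guideline), overlap has 3–31% power for a 20% bias. For a 30% bias it has 3–85%, the high end needing small error and intake near or above the guideline. For a 10% bias the log ratio itself has only 75%, 42% and 26% at e = 0.2, 0.3 and 0.4.

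**The case against.** The strongest reply has five parts.

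- *Silence is not exclusion.* A reader might infer that the plan restricts subgroups to the three-colour scale. It does not say so. Section 8 gives no subgroup method for any outcome, and the retest correlation may be on grams. This stands: the fault is that nothing suitable is specified.
- *The stated aim is usability.* Misreporting is one reason given for expecting subgroup differences, not the quantity to be estimated. This also stands, but the reason is the plan's own and no planned statistic addresses it.
- *The colours keep direction.* Only the collapse to match or no match loses it. This stands: a signed colour comparison recovers much of the power (51–92% above). It supports reporting direction as well, but Section 8 does not plan that, and grams still do better.
- *A level-driven gap in agreement is partly a real result.* Users see the colour, and a subgroup close to a cut-off does get more mismatched colours. This stands. The gap misleads only if read as a gap in measurement accuracy.
- *The power figures rest on assumed inputs.* No subgroup test, alpha or SD is planned. Log ratios fail where intake is zero, which is plausible over four recall days for foods such as fish or legumes, and the power figures do not carry over to raw grams. This stands as a limit on the numbers. It does not affect the correlation argument.

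**Conclusion.** The concern holds in limited form. The plan gives possible misreporting as a reason for its subgroup analyses but specifies no signed Nutri+ versus Compl-Eat difference by subgroup. Correlations cannot show a constant bias. For a relative bias up to about 20%, comparing overlap has low power, roughly 5 to 26% under the stated assumptions, against 79% to over 99% for the log ratio. Overlap can also differ by about 7 points (68.7% v 75.6%), or more, through intake level alone.

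Two stronger readings are not supported. One is that the evaluation has almost no power whatever the bias: a 30% bias can be detected when error is small, and all the figures depend on variances that the documents do not give. The other is that a subgroup could pass or fail the 75% goal: Section 8 sets that goal per product group, not per subgroup.

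The change is worth making before analysis. It concerns a stated purpose of recruitment, not the overall main objective, and Section 9 already accepts that subgroup analyses may prove infeasible.

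**What to change.** In Sections 6 and 8:

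1. For each of the 17 quantified product groups, add the Nutri+ minus Compl-Eat gram difference by sex, age, education and BMI. Use the log ratio where zeros are rare, and raw grams with a bootstrap interval otherwise. Report the between-subgroup difference with a 95% confidence interval, labelled exploratory. Moving subgroups to the gram correlation already planned would not be enough, since it too misses a constant bias.
2. Keep subgroup percentage agreement, but show it as a 3×3 table giving the direction of misclassification, beside each subgroup's colour distribution. State that a gap in agreement alone will not be read as a difference in measurement accuracy.
3. State that the gram estimate is bias relative to Compl-Eat and cannot show misreporting shared by both methods.

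Cost: wording in two sections and a little more analysis, with no new data. With one contrast per factor there are 17 × 4 = 68 exploratory estimates, best reported as intervals and not as a list of significance tests.

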- To investigate whether the results of the Nutri+ module are reproducible over time or whether time effects are present, with a correlation coefficient of ≥ 0.75 between two measurement points considered successful.
- To evaluate the Nutri+ module (dietary questionnaire) against the Compl-Eat 24-hour recall method. Specifically, we aim to examine whether the Nutri+ module can accurately classify at least 75% of individuals into three categories for the 21 product groups.
- To evaluate the visualization of the profile wheel by users of the Nutri+ module.

3 Study design

This is a longitudinal randomized study to evaluate the Nutri+ dietary intake module. The Nutri+ module can be completed by participants at home via an online portal; it is filled out only once and takes approximately 30 minutes to complete. As a reference method, Compl-Eat is used. This is an online 24-hour recall method developed by Wageningen University & Research (Meijboom et al., 2017). Participants in the study can complete this 24-hour recall themselves at home via a portal, recording everything they ate and drank in the previous 24 hours. Based on the submitted data, the Compl-Eat platform can determine for an individual how much and what was consumed at both the product group and individual product levels. Compl-Eat is completed by participants on four non-consecutive days—three weekdays and one weekend day (Saturday or Sunday)—to obtain an accurate representation of an individual's average intake. The 24-hour recalls are manually checked for completeness by a researcher afterwards.

A randomized cross-over design is used, in which one group of participants completes the Nutri+ module first, while the other group completes Compl-Eat first. The days on which participants complete

the Nutri+ questionnaire and the days on which Compl-Eat is completed are randomly selected. There is a minimum interval of 7 days between the Nutri+ module and the first or last day of Compl-Eat.

In addition, possible time effects in dietary recording and the reproducibility of the Nutri+ module results are examined. To this end, participants are invited again after three to six months to repeat the entire procedure of completing the Nutri+ module once and Compl-Eat four times. The first series of questionnaires is sent out in April; the second series begins in September.

See Figure 2 for a schematic overview of the study design.

[figure not shown]

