The second phase involves recruiting participants through social media campaigns and the completion of the Nutri+ module and Compl-Eat. Participants are recruited via social media advertisements, which link them to an online information sheet. After reading the information sheet, participants can provide online informed consent for participation in the study. They are then automatically directed to an online screening questionnaire (see inclusion and exclusion criteria). This screening questionnaire automatically assesses whether the individual meets the study's selection criteria. Candidates who do not meet the criteria are informed immediately. Candidates who do meet the criteria are directed to a baseline questionnaire to collect various baseline data (medication use, physical activity, adherence to any dietary or nutritional rules, and allergies or intolerances). Participants are then informed about the further study schedule and procedures.

The study uses a cross-over design, in which participants are randomly assigned to one of two sequences: starting with the Nutri+ module or starting with Compl-Eat. Participants who start with the Nutri+ module during the first series (autumn 2022) will start with Compl-Eat during the second series (spring 2023), and vice versa.

For all participants, the days on which the Nutri+ module and Compl-Eat must be completed are randomly selected. Both the Nutri+ module and Compl-Eat are completed at home using login credentials for the respective online platforms. Participants are not informed of the full schedule in advance to minimize potential influence on their dietary behavior. One day before a participant's first "assessment day," they are contacted by email by a researcher, requesting that they complete either the Nutri+ module or Compl-Eat the following day. Participants can respond to this email if the scheduled day does not fit their personal planning. In that case, the researcher reschedules the assessment day, and the participant is contacted again at a later time.

During the first series (autumn 2022), all participants complete Compl-Eat on four days within a two-week period and complete the Nutri+ module once. A minimum interval of seven days is maintained between completing Compl-Eat and the Nutri+ module to prevent interference between the methods.

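### Compl-Eat days are averaged without weekday/weekend weights, and the plan does not say whether the three-plus-one split means days eaten or days completed; mean reference grams may be modestly biased

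*Combined protocol and SAP*

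**What the plan says.** Section 3 (Study design) fixes the reference schedule: "Compl-Eat is completed by participants on four non-consecutive days—three weekdays and one weekend day (Saturday or Sunday"). The stated purpose is "to obtain an accurate representation of an individual's average intake". The same section describes participants as "recording everything they ate and drank in the previous 24 hours".

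Section 5 (Second Phase) says that "the days on which the Nutri+ module and Compl-Eat must be completed are randomly selected", with the four Compl-Eat days falling inside two weeks. The day before a participant's first assessment day, a researcher writes "requesting that they complete either the Nutri+ module or Compl-Eat the following day". An assessment day is therefore the day on which the tool is filled in.

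Section 8 (Data-analysis and statistics) states for Compl-Eat that "all analyses will be based on the average intake per product group across the four assessment days" of a series. It gives no weights and no usual-intake model, and the rest of the document adds none.

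The main objective (Section 2) is whether absolute grams are comparable, including the percentage of intake that Nutri+ covers. The primary outcome (Section 6) is "Intake in grams for the 17 product groups that are quantitatively assessed", a list that includes alcohol, soft drinks, party snacks, fast food and desserts.

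**The concern.** A schedule stratified by day type is analysed as if three to one were the calendar ratio. A week has five weekdays to two weekend days, or 2.5 to one. With four equal weights the weekend gets 1/4 rather than 2/7, so the Compl-Eat mean would not estimate average intake over a week, although the schedule was chosen for that purpose. Any resulting bias is systematic: more participants do not reduce it.

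The comparison of absolute grams and the percentage covered are exposed directly, because a shifted Compl-Eat mean is the denominator. Section 5 says that the analysis will lead to recommendations on the questionnaire, algorithms and cut-off values, so an artefact in the reference could be carried into the tool.

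The plan also leaves open which days the split describes. A recall filled in on a Saturday covers mostly Friday, and one filled in on a Monday covers mostly Sunday. The size of the bias depends on this.

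**Working it through.** The plan states no weekend weight and no bias figure, so there is nothing to reproduce. The inputs from the documents are the 3 + 1 split, the unweighted four-day average, the 24-hour look-back, the two-week window and the target of 200 participants. The ratio r of weekend-day to weekday intake is **an assumption**, because the documents give no such intakes.

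**1. Split refers to days eaten.** Set weekday intake to 1 and weekend intake to r.

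- Plain mean: (3 + r)/4. Calendar mean: (5 + 2r)/7.
- Relative bias: 7(3 + r)/[4(5 + 2r)] - 1.
- Absolute bias: 1/4 - 2/7 = -1/28 of the weekend-minus-weekday difference.

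**2. Split refers to completion days, with the day eaten taken as the day before.** The weekend completion day is Saturday (eaten Friday) or Sunday (eaten Saturday), so it gives a weekend intake day with probability 1/2. Each weekday completion gives one with probability 1/5 (Monday, eaten Sunday). The expected share is (0.5 + 3 × 0.2)/4 = 27.5%. The relative bias is (0.725 + 0.275r)/[(5 + 2r)/7] - 1.

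| r | bias, days eaten (25%) | bias, completion days (27.5%) |
|---|---|---|
| 0.5 | +2.1% | +0.6% |
| 1 | 0 | 0 |
| 1.5 | -1.6% | -0.5% |
| 2 | -2.8% | -0.8% |
| 3 | -4.5% | -1.4% |
| 5 | -6.7% | -2.0% |
| weekend only | -12.5% | -3.8% |

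**3. Spread between participants on the completion-day reading.** All sets of three weekdays and one weekend day in a 14-day window, with no two days adjacent, were enumerated. Sets were taken as equally likely for each starting weekday, and starting weekdays as equally likely. The mean weekend share is again 27.5% (26% to 31% by starting weekday). The number of weekend days eaten is 0 in about 17% of schedules, 1 in 56%, 2 in 26% and 3 in under 1%. At r = 3 the calendar mean is 11/7 = 1.571. A plain mean with no weekend day is expected to be 1/1.571 - 1 = -36% off, and one with two weekend days 2/1.571 - 1 = +27% off.

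**4. Precision cost of 5/7 and 2/7 weights, with three weekdays and one weekend day eaten.** Each weekday gets 5/21 and the weekend day 2/7.

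- Equal day variances: 3(5/21)² + (2/7)² = 0.2517, against 0.2500. The standard error rises by √(0.2517/0.2500) - 1 = 0.3%.
- Day SD proportional to the day mean (assumed): the weighted variance is proportional to 0.1701 + 0.0816r² and the plain variance to (3 + r²)/16. At r = 2 these are 0.4966 and 0.4375, so the standard error rises by 6.5%. At r = 3 they are 0.9048 and 0.7500, a rise of 9.8%.

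**5. Bias against variance at r = 3, days-eaten reading, with day SD equal to the day mean (assumed).** The bias is 1.5 - 1.571 = -0.0714, and its square is 0.0051.

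- One participant: mean squared error is 0.750 + 0.0051 = 0.755 plain, against 0.905 weighted. The plain mean is better.
- Group of 200: 0.750/200 + 0.0051 = 0.0089 plain, against 0.905/200 = 0.0045 weighted. The weighted mean is better. Only day-to-day variation is counted here.

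**The case against.** The strongest reply is that 25% is not established. The wording concerns days of completion, and on that reading the expected share is 27.5% against 28.6%, so most of the mean bias disappears. This stands, and it limits the point. It does not remove it, because the plan never says which reading applies, and the completion-day reading leaves the mix of days uneven between participants.

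Second, Section 8 examines grams through correlation coefficients and calls these outcomes mainly exploratory. A near-proportional shift barely changes a correlation, and reproducibility rests on Nutri+ alone. This also stands. What remains exposed is the absolute-gram comparison and the percentage covered, both named in the main objective.

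Third, a reader might infer that 5/7 and 2/7 weights should replace the plain mean for every participant and every analysis at negligible cost. Three results speak against that. The per-person formula is undefined without a weekend intake day, which on the completion-day reading happens in about 17% of schedules even with complete data. A cost below 1% requires equal day variances. Weighting can also make an individual's estimate less accurate (0.755 against 0.905 in step 5).

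Fourth, every ratio is assumed. That is correct, and the documents do not show which product groups are weekend-heavy.

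**Conclusion.** The point holds as a modest one about the reference mean. On the days-eaten reading the weekend counts 25.0% rather than 28.6%, with a bias of -1.6% to -4.5% at assumed ratios of 1.5 to 3 and a limit of -12.5%. On the completion-day reading the mean bias is -0.5% to -1.4% at the same ratios. The main defect is then the uneven number of weekend intake days per person. The sign reverses for foods eaten less at weekends.

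A reader might go further and conclude that a correct Nutri+ would be seen to over-report alcohol, snacks or fast food, or that participants near a cut-off would be given the wrong colour. The documents do not support either as a finding: they give no weekend/weekday ratios, and the amount of misclassification has not been estimated.

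The case for weighting is good for group-level grams and percentage covered. For individual classification and for correlations it is a trade-off, and the plain mean is defensible.

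**What to change.** In Section 8:

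1. State that each recall is labelled weekday or weekend by the day eaten, and say in Section 3 whether the three-plus-one split means days eaten or days completed. Report how many weekend intake days participants have in each series.
2. For the absolute-gram and percentage-of-intake-covered comparisons, define the Compl-Eat mean within each series as 5/7 × pooled weekday mean + 2/7 × pooled weekend mean. Pooling at group level lets participants without a weekend intake day still contribute. Standard errors should allow for several recalls from one person, for example by resampling participants.
3. For the three-colour classification and the correlations, keep the plain four-day mean. Report the weighted version as a sensitivity analysis in participants with both day types.

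This needs a few sentences and a little code, and no new data if the recall date is stored. The price is some precision. With three weekdays and one weekend day eaten, the standard error from day-to-day variation rises by about 0.3% with equal day variances, and by about 6% to 10% if day SD is proportional to the mean at ratios of 2 to 3.
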